10.2 Sample Size and Accrual

A total of 92 evaluable STS patients is required to detect 55% vs 66% with 80% power and an alpha level of 10%. If 32 out of the first 55 patients are alive and progression free at 12 weeks, this trial may enroll up to 108 STS patients in order to accrue a total of 92 evaluable patients. If the trial has not yet achieved 32 responses, may be suspended to enrollment to allow the 55th patient to reach week 12 of treatment for evaluation.

In addition, up to 36 patients with osteosarcoma and 20 patients with liposarcoma will be enrolled to obtain exploratory information for patients with these two histologies. Data exists to help construct baseline event free survival outcomes that can be used as a comparison for future phase II trials for recurrent osteosarcoma ([J Clin Oncol](#). 2016 Sep 1;34(25):3031-8. doi: 10.1200/JCO.2015.65.5381. Epub 2016 Jul 11.)

Using a single arm, 2 stage Phase II trial design: For stage I- If 4 or more of 19 patients have disease control of greater than 4 months then Stage 2 should be opened. The endpoint is that if 11 or more patients/ 36 have disease control at 4 months, then the agent is considered sufficiently efficacious for additional study.

As the study has been using 12 week and 20 week endpoints, we can use 20 weeks instead of 16 weeks as a surrogate endpoint.

The DMC reviewed the interim analysis data on 1/11/2017, and has approved cohort 1 to reopen to 96 total patients(to obtain 92 evaluable patients). In addition, based on the percentage of non-evaluable patients during the interim analysis, it was determined that a total of 108 patients would most likely need to be enrolled in order to obtain 92 evaluable patients.

The remaining slots have been equally divided in 5 ways among the sites, with an expiration date of May 12, 2017. Status of accrual will be reassessed at that time, and the remaining slots will be divided accordingly.

The 16 additional osteosarcoma slots will only be available at Northwestern (NMH).

10.3 Data Analyses Plans

PFR and OS will be estimated for each histologic group (STS, osteosarcoma, and liposarcoma) using Kaplan-Meier methods. Response rates will be summarized by the observed proportion of patients with response, along with a 95% confidence interval. Toxicities will be tabulated and summarized by the number of patients experiencing each toxicity. A formal hypothesis test for the median PFR of the STS patients is planned; no formal hypothesis test is planned for the other two histologic groups.

11.0 STUDY MANAGEMENT

11.1 Institutional Review Board (IRB) Approval and Consent

It is expected that the IRB will have the proper representation and function in accordance with federally mandated regulations. The IRB should approve the consent form and protocol.

In obtaining and documenting informed consent, the investigator should comply with the applicable regulatory requirement(s), and should adhere to Good Clinical Practice (GCP) and to ethical principles that have their origin in the Declaration of Helsinki.

Before recruitment and enrollment onto this study, the patient will be given a full explanation of the study and will be given the opportunity to review the consent form. Each consent form must include all the relevant elements currently required by the FDA Regulations and local or state regulations. Once this essential information has been provided to the patient and the investigator is assured that the patient understands the implications of participating in the study, the patient will be asked to give consent to participate in the study by signing an IRB approved consent form.

Prior to a patient's participation in the trial, the written informed consent form should be signed and personally dated by the patient and by the person who conducted the informed consent discussion.

For patients with limited English proficiency who are approached for participation in the study, an IRB approved short form will be used. In addition, the services of an interpreter fluent in both English and the language understood by the potential study patient will be obtained. The patient will be re-consented using the IRB approved translated consent in the language understood by the patient, when available. The exact process will be conducted in accordance to local IRB guidelines and policies.

11.2 Amendments

The Principal Investigator will formally initiate all amendments to the protocol and/or informed consent. All amendments will be subject to the review and approval of the appropriate local, institutional, and governmental regulatory bodies, as well as by GlaxoSmithKline. Amendments will be distributed by the lead institution (Northwestern) to all affiliate sites upon approval by the Northwestern University IRB.

11.3 Registration Procedures

Patients may not begin protocol treatment prior to registration. All patient registrations will be registered centrally through the Clinical Research Office at Northwestern University before enrollment to study. Please contact the assigned Quality Assurance Monitor (QAM) or email the QA Department ([contact]) for questions regarding patient registration.

Prior to registration, eligibility criteria must be confirmed by the assigned QAM. The study coordinator will screen all subjects for potential registration via the web-based application NOTIS (Northwestern Oncology Trial Information System), which is available at: <https://notis.nubic.northwestern.edu>. Please note that a username and password is required to use this program, and will be provided during site activation prior to training on the NOTIS system.

BEFORE a patient can be treated on study, please complete and submit the following items to confirm eligibility and receive an identification number:

- Patient's signed and dated informed consent form (upload to NOTIS and keep original hard copy in a secure location/study chart)
- Eligibility checklist (signed and dated by the treating physician – upload to NOTIS)
- Eligibility eCRF (complete in NOTIS)
- Copy of the pathology report (upload to NOTIS)

Training on eCRF completion will be provided at the time of site activation.

IRB #: STU00200112 Approved by NU IRB for use on or after 9/2/2020 through 8/16/2021.
The QAM will review the registration, register the patient, assign a subject identification number, and send a confirmation of registration to study personnel. Registration will then be complete and the patient may begin study treatment.

11.4 Data Submission

Once a subject is confirmed and registered to the study, eCRFs should be submitted according to the detailed data submission guidelines (provided in a separate document). Please see the data submission guidelines located on the protocol page in NOTIS.

Please contact [contact] for further details

11.5 Instructions for Participating Sites

Before the study can be initiated at any site, the following documentation must be provided to the Clinical Research Office at Northwestern University:

- Signed and completed Participating Site Questionnaire to participate in the study.
- Signed copy of Northwestern University's Data Monitoring Committee policy pertaining to data submission.
- Draft informed consent form should for review/approval prior to submission to the local IRB
- A copy of the official IRB approval letter for the protocol and informed consent.
- CVs and medical licensure for the local PI and any sub-investigators who will be involved in the study at the site.
- Form FDA 1572 appropriately filled out and signed with appropriate documentation.

Additional activities may be required prior to site activation (i.e. contract execution, study- specific training). Full requirements will be outlined in a memo upon receipt of the signed Participating Site Questionnaire.

11.6 Data Management and Monitoring/Auditing

This study will be conducted in compliance with the Data Safety Monitoring Plan (DSMP) of the Robert H. Lurie Comprehensive Cancer Center of Northwestern University:

<http://cancer.northwestern.edu/CRO/data/DataandSafetyMonitoringPlanMay2014.pdf>

The level of risk attributed to this study requires high-intensity monitoring as outlined in the DSMP. The assigned QAM, with oversight from the Data Monitoring Committee, will monitor this study in accordance with the study phase and risk level. Please refer to the Appendices for additional data submission instructions.

11.7 Adherence to the Protocol

Except for an emergency situation in which proper care for the protection, safety, and well-being of the study patient requires alternative treatment, the study shall be conducted exactly as described in the approved protocol.

11.7.1 Emergency Modifications

Investigators may implement a deviation from, or a change of, the protocol to eliminate an immediate hazard(s) to trial subjects without prior IRB approval.

For any such emergency modification implemented, an IRB modification form must be completed within 5 business days of making the change, and the QAM must be notified within 24 hours of such change.

11.7.2 Other Protocol Deviations

A protocol deviation is any unplanned variance from an IRB approved protocol that:

- Is generally noted or recognized after it occurs.
- Has no substantive effect on the risks to research participants.
- Has no substantive effect on the scientific integrity of the research plan or the value of the data collected.
- Did not result from willful or knowing misconduct on the part of the investigator(s).

A protocol deviation may be considered an instance of Reportable New Information (RNI) if it:

- Has harmed or increased the risk of harm to one or more research participants.
- Has damaged the scientific integrity of the data collected for the study.
- Results from willful or knowing misconduct on the part of the investigator(s).
- Demonstrates serious or continuing noncompliance with federal regulations, State laws, or University policies.

11.8 Investigator Obligations

The Principal Investigator is responsible for the conduct of the clinical trial at the site in accordance with Title 21 of the Code of Federal Regulations and/or the Declaration of Helsinki. The PI is responsible for personally overseeing the treatment of all study patients. The PI must assure that all study site personnel, including sub-investigators and other study staff members, adhere to the study protocol and all FDA/GCP/NCI regulations and guidelines regarding clinical trials both during and after study completion.

The Principal Investigator at each institution or site will be responsible for assuring that all the required data will be collected, entered onto the appropriate eCRFs, and submitted within the study-specific timeframes. Periodically, monitoring visits may be conducted and the Principal Investigator will provide access to his/her original records to permit verification of proper entry of data. The study may also be subject to routine audits by the Audit Committee, as outlined in the DSMP.

11.9 Publication Policy

All potential publications and/or data for potential publications (e.g. manuscripts, abstracts, posters, clinicaltrials.gov releases) must be approved in accordance with the policies and processes set forth in the Lurie Cancer Center DSMP. The assigned QAM will prepare a preliminary data summary (to be approved by the DMC) no later than 3 months after the study reaches its primary completion date (the date that the final subject is examined or receives an intervention for the purposes of final data collection for the primary endpoint). If the investigator's wish to obtain DMC-approved data prior to this point (or prior to the point dictated by study design), the PI must send a written request for data to the QAM which includes justification. If the request is approved, data will be provided no later than 4 weeks after this request approval. The data will be presented to the DMC at their next available meeting, and a final, DMC-approved dataset will be released along with any DMC decisions regarding publication. The investigators are expected to use only DMC-approved data in future publications. The investigators should submit a copy of the manuscript to the biostatistician to confirm that the DMC-approved data are used appropriately. Once the biostatistician gives final approval, the manuscript may be submitted to external publishers.

REFERENCES

APPENDIX A1. GENERAL DRUGS TO BE AVOIDED WITH PAZOPANIB

- CYP3A4 STRONG INHIBITORS
- CYP3A4 STRONG INDUCERS
- CYP SUBSTRATES
- SIMVASTATIN (USED WITH CAUTION)
- PROTON PUMP INHIBITORS AND H2 RECEPTOR BLOCKERS

APPENDIX A2. Table of Drugs known to be metabolized by CYP450 isoenzymes 2D6 and 3A4 (to be avoided with pazopanib)

| CYP3A3/4 | |
|-----------------------|--|
| Substrates | |
| Acetaminophen | Chlorpromazine |
| Aifentanil | Cimetidine |
| Alosetron | Cisapride |
| Alprazolam | Citalopram |
| Amiodarone | Clarithromycin |
| Amitriptyline (minor) | Clindamycin |
| Amlodipine | Clomipramine |
| Anastrozole | Clonazepam |
| Androsterone | Clozapine |
| Antipyrine | Cocaine |
| Astemizole | Codeine (demethylation) |
| Atorvastatin | Cortisol |
| Benzphetamine | Cortisone |
| Bepidil | Cyclobenzaprine (demethylation) |
| Bexarotene | Cyclophosphamide |
| Bromazepam | Cyclosporine |
| Bromocriptine | Dapsone |
| Budesonide | Dehydroepiandrosterone |
| Bupropion (minor) | Delavirdine |
| Buspirone | Desmethyldiazepam |
| Busulfan | Dexamethasone |
| Caffeine | Dextromethorphan (minor, N-demethylation) |
| Cannabinoids | Diazepam (minor; hydroxylation, N-demethylation) |
| Carbamazepine | Nefazodone |
| Cevimeline | Nelfinavir |
| Cerivastatin | Nevirapine |
| Digitoxin | Nicardipine |
| Diltiazem | Nifedipine |
| Disopyramide | Niludipine |
| Docetaxel | Nimodipine |
| Dolasetron | Nisoldipine |
| Donepezil | Nitrendipine |
| Doxorubicin | |
| Doxycycline | |

| | |
|-------------------------------|--------------------------|
| Dronabinol | Omeprazole (sulfonation) |
| Enalapril | Ondansetron |
| Erythromycin | Oral contraceptives |
| Estradiol | Orphenadrine |
| Ethinyl estradiol | Paclitaxel |
| Ethosuximide | Pantoprazole |
| Etoposide | Pimozide |
| Exemestene | Pioglitazone |
| Dofetilide (minor) | Pravastatin |
| Felodipine | Prednisone |
| Fentanyl | Progesterone |
| Fexotenadine | Proguanil |
| Finaxteride | Propafenone |
| Fluoxetine | Quercetin |
| Flutamide | Quetiapine |
| Glyburide | Quinidine |
| Granisetron | Quinine |
| Halofantrine | Repaglinide |
| Hydrocortixone | Retinoic acid |
| Hydroxyarginine | Rifampin |
| Ifosfamide | Risperidone |
| Imipramine | Ritonavir |
| Indinavir | Salmeterol |
| Isradipine | Saquinavir |
| Itraconazole | Sertindole |
| Ketoconazole | Sertraline |
| Lansoprazole | Sibutramine |
| Letrozole | Sildenafil citrate |
| Levobupivacaine | Simvastatin |
| Lidocaine | Sirolimus |
| Loratadine | Sufentanil |
| Losartan | Tacrolimus |
| Lovastatin | Tamoxifen |
| Methadone | Temazepam |
| Mibefradil | Teniposide |
| Miconazole | Terfenadine |
| Midazolam | Testosterone |
| Mifepristone | Tetrahydrocannabinol |
| Mirtazapine (N-demethylation) | Theophylline |
| Montelukast | Tiagabine |
| Navelbine | Tolterodine |
| Toremifene | Vincristine |
| Trazodone | Warfarin (R-warfarin) |
| Tretinoin | Yohimbine |
| Triazolam | Zaleplon (minor pathway) |
| Troglitazone | Zatoestron |
| Troleandomycin | Zileuton |
| Venlafaxine (N-demethylation) | Ziprasidone |
| Verapamil | Zolpidem |
| Vinblastine | Zonisamide |

| Inducers | |
|------------------------|-------------------------------|
| Carbamazepine | Phenytoin |
| Dexamethasone | Primidone |
| Ethosuximide | Progesterone |
| Glucocorticoids | Rifabutin |
| Griseofulvin | Rifampin |
| Nafcillin | Rofecoxib (mild) |
| Nelfinavir | St John's wort |
| Nevirapine | Sulfadimidine |
| Oxcarbazepine | Sulfinpyrazone |
| Phenobarbital | Troglitazone |
| Phenylbutazone | |
| Inhibitors | |
| Amiodarone | Ketoconazole |
| Anastrozole | Metronidazole |
| Atazanavir | Mibefradil |
| Azithromycin | Miconazole (moderate) |
| Cannabinoids | Nefazodone |
| Cimetidine | Nelfinavir |
| Clarithromycin | Nevirapine |
| Clotrimazole | Norfloxacin |
| Cyclosporine | Norfluoxetine |
| Danazol | Omeprazole (weak) |
| Delavirdine | Oxiconazole |
| Dexamethasone | Paroxetine (weak) |
| Diethyldithiocarbamate | Propoxyphene |
| Diltiazem | Quinidine |
| Dirithromycin | Quinine |
| Disulfiram | Quinupristin and dalfopristin |
| Entacapone (high dose) | Ranitidine |
| Erythromycin | Ritonavir |
| Ethinyl estradiol | Saquinavir |
| Fluconazole (weak) | Sertindole |
| Fluoxetine | Sertraline |
| Fluvoxamine | Telithromycin |
| Gestodene | Troglitazone |
| Grapefruit juice | Troleandomycin |
| Indinavir | Valproic acid (weak) |
| Isoniazid | Verapamil |
| Itraconazole | Voriconazole |
| | Zafirlukast |
| | Zileuton |

(Adapted from Cytochrome P-450 Enzymes and Drug metabolism. In : Lacy CF, Armstrong LL, Goldman MP, Lance LL eds. Drug Information Handbook 8th ed. Hudson, OH; LexiComp Inc. 2000: 1364-1371)

APPENDIX B. TABLE OF ORAL TOPOTECAN DRUG INTERACTIONS

| |
|--|
| Breast Cancer Resistance Protein (ABCG2, BCRP, MXR) Inhibitors and Inducers |
| Antiestrogens: tamoxifen, toremifene |
| Antiretrovirals, Protease inhibitors: ritonavir, nelfinavir, saquinavir |
| Proton pump inhibitors: pantoprazole, omeprazole |
| Others: diethylstilbesterol, estrone, flavopiridol, novobiocin, reserpine, carbamazepine |
| P-glycoprotein (ABCB1, P-gp, MDR1) Inhibitors and Inducers |
| Antifungals: Itraconazole, etraconazole, ketoconazole, clotrimazole |
| Antiretrovirals, Protease inhibitors: amprenavir, indinavir, ritonavir, nelfinavir, saquinavir |
| Antibiotics: erythromycin, rifampin |
| Calcium channel blockers: diltiazem, nicardipine, verapamil |
| Anticonvulsants: carbamazepine, phenobarbital |
| Analgesics: meperidine, methadone, morphine, pentazocine |
| Immune modulators: Valspodar |
| Others: Atorvastatin, bromocriptine, carvedilol, omeprazole, progesterone, quinine, dexamethasone (large doses), phenothiazine, retinoic acid, St. John's wort |

APPENDIX C. NEW YORK HEART ASSOCIATION (NYHA) FUNCTIONAL CLASSIFICATION

The **New York Heart Association (NYHA) Functional Classification** provides a simple way of classifying the extent of [heart failure](#). It places patients in one of four categories based on how much they are limited during physical activity; the limitations/symptoms are in regards to normal breathing and varying degrees in shortness of breath and or angina pain:

| Functional Capacity | Objective Assessment |
|---|---|
| 
Class I. Patients with cardiac disease but without resulting limitation of physical activity. Ordinary physical activity does not cause undue fatigue, palpitation, dyspnea or anginal pain.
 | 
No objective evidence of cardiovascular disease
 |
| 
Class II. Patients with cardiac disease resulting in slight limitation of physical activity. They are comfortable at rest. Ordinary physical activity results in fatigue, palpitation, dyspnea or anginal pain.
 | 
Objective evidence of minimal cardiovascular disease
 |
| 
Class III. Patients with cardiac disease resulting in marked limitation of physical activity. They are comfortable at rest. Less than ordinary activity causes fatigue, palpitation, dyspnea or anginal pain.
 | 
Objective evidence of moderately severe cardiovascular disease
 |
| 
Class IV. Patients with cardiac disease resulting in inability to carry on any physical activity without discomfort. Symptoms of heart failure or the anginal syndrome may be present even at rest. If any physical activity is undertaken, discomfort increases.
 | 
Objective evidence of severe cardiovascular disease
 |

APPENDIX D – DATA COLLECTION & SUBMISSION GUIDELINES

Please see the data submission guidelines located on the protocol page in NOTIS.

APPENDIX E – DATA SAFETY MONITORING PLAN

<http://cancer.northwestern.edu/CRO/data/DataandSafetyMonitoringPlanMay2014.pdf>

Note: Link inserted in appropriate sections

APPENDIX F- PATIENT MEDICATION DIARY

NU 14S03: Topotecan

Dispensed date: ____ Patient's Study ID _____ Patient's Initials ____ Cycle # _____

Instructions to the Patient:

1. You will take capsules of topotecan by mouth once a week for the first three weeks. On the fourth week you will not take topotecan.
2. You should swallow the capsules whole with at least 1 cup (8 ounces) of water, with or without food.
3. If you vomit on a day where you take both medications, you will take your next dose of topotecan one week later and your next dose of pazopanib the following day.

| Topotecan dose: _____ mg | | | |
|--------------------------|------|---|---|
| Day | Date | Time Taken | Comments (please note if you vomit/and any other symptoms you experience) |
| 1 | | ____ a.m. ____ p.m. | |
| 2 | | DO NOT TAKE TOPOTECAN ON THESE DAYS. | |
| 3 | | | |
| 4 | | | |
| 5 | | | |
| 6 | | | |
| 7 | | | |
| 8 | | | |
| 9 | | DO NOT TAKE TOPOTECAN ON THESE DAYS. | |
| 10 | | | |
| 11 | | | |
| 12 | | | |
| 13 | | | |
| 14 | | | |
| 15 | | ____ a.m. ____ p.m. | |
| 16 | | DO NOT TAKE TOPOTECAN ON THESE DAYS. | |
| 17 | | | |

| | | |
|----|--|---|
| 18 | | DO NOT TAKE TOPOTECAN ON THESE DAYS. |
| 19 | | |
| 20 | | |
| 21 | | |
| 22 | | |
| 23 | | |
| 24 | | |
| 25 | | |
| 26 | | |
| 27 | | |
| 28 | | |

Physician's office will complete this section:

1. Total # of pills dispensed: _____
2. Total # of pills taken this cycle: _____
3. Total # of pills returned: _____
4. Patient's signature: _____ Date: _____
5. Reviewer's signature: _____ Date: _____

NU 14S03 Medication Diary: Pazopanib

Dispensed date: _____ Patient's Study ID _____ Patient's Initials ____ Cycle# _____

Instructions to the Patient:

1. Take pazopanib by mouth 1 time every day at about the same time each day. Take it on an empty stomach (at least 1 hour before and 2 hour after eating) with about 1 cup (8 ounces) of water.
2. If you vomit on a day where you only take pazopanib, the next dose would be the following day. If you vomit on a day where you take both medications, you will take your next dose of topotecan one week later and your next dose of pazopanib the following day.

| Pazopanib ___ mg once daily | | | |
|-----------------------------|------|----------------------|---|
| Day | Date | Time Taken | Comments (please note if you vomit/and any other symptoms you experience) |
| 1 | | ___ a.m. ___ p.m. | |
| 2 | | ___ a.m. ___ p.m. | |
| 3 | | ___ a.m. ___ p.m. | |
| 4 | | ___ a.m. ___ p.m. | |
| 5 | | ___ a.m. ___ p.m. | |
| 6 | | ___ a.m. ___ p.m. | |
| 7 | | ___ a.m. ___ p.m. | |
| 8 | | ___ a.m. ___ p.m. | |
| 9 | | ___ a.m. ___ p.m. | |
| 10 | | ___ a.m. ___ p.m. | |
| 11 | | ___ a.m. ___ p.m. | |
| 12 | | ___ a.m. ___ p.m. | |
| 13 | | ___ a.m. ___ p.m. | |
| 14 | | ___ a.m. ___ p.m. | |
| 15 | | ___ a.m. ___ p.m. | |
| 16 | | ___ a.m. ___ p.m. | |
| 17 | | ___ a.m. ___ p.m. | |

| | | | |
|----|--|------------------------|--|
| 18 | | ____ a.m. ____ p.m. | |
| 19 | | ____ a.m. ____ p.m. | |
| 20 | | ____ a.m. ____ p.m. | |
| 21 | | ____ a.m. ____ p.m. | |
| 22 | | ____ a.m. ____ p.m. | |
| 23 | | ____ a.m. ____ p.m. | |
| 24 | | ____ a.m. ____ p.m. | |
| 25 | | ____ a.m. ____ p.m. | |
| 26 | | ____ a.m. ____ p.m. | |
| 27 | | ____ a.m. ____ p.m. | |
| 28 | | ____ a.m. ____ p.m. | |

Physician's office will complete this section:

1. Total # of pills dispensed: _____
2. Total # of pills taken this cycle: _____
3. Total # of pills returned: _____
4. Patient's signature: _____
Date: _____
5. Reviewer's signature: _____
Date: _____

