4.0 TREATMENT PLAN

4.1 Overview

Patients will take oral pazopanib (800mg starting dose) once daily AND oral toptecan (8 mg starting dose) on days 1, 8, and 15 of each 28 day cycle. Treatment will continue until disease progression or unacceptable toxicity occurs, or until discontinuation per patient preference or physician recommendation. Patients who are removed from study treatment for toxicity should be followed until toxicity resolves to grade 1 or baseline. Patients **with PD** at end of treatment will be followed every 6 months for 2 years (or until death) for survival. Patients **without PD** at end of treatment will be followed every 6 months for 5 years (or until death) for survival and progression.

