4.2.1 Study Drug Administration

Patients will receive pazopanib at a dose of 800 mg/day (4 x 200mg tablets). Pazopanib should be taken orally, without food, at least one hour before or two hours after a meal, with up to 200 mL of water. Patients will concurrently receive topotecan 8 mg (8 x 1-mg capsules) to be taken orally on day 1, 8, and 15 of a 28 day cycle. Topotecan can be taken with or without food. Cycles will be repeated every 4 weeks.

On days of a scheduled clinic visit, the dose of pazopanib and topotecan should be taken *after* visit procedures are completed. Treatment with pazopanib and topotecan will continue if tolerated and in the absence of documented disease progression or unacceptable toxicity. If a dose is vomited or if a dose is missed for any reason, the dose should not be made up. Patients will be given a medication diary to record all doses taken, doses missed, and daily adverse events experienced. This will be collected and reviewed at study visits.

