- h. Complete Blood Count (CBC): Performed on day 1 and 15 of cycles 1 and 2 (+/- 3 days) then day 1 of each cycle (+/-3 days). For patients experiencing significant cytopenias felt possibly related to Topotecan, CBCs should be obtained more frequently (weekly or more frequently) to assess timing for retreatment or need for G-CSF or transfusion support.
- i. Patients **with PD** at end of treatment will be followed every 6 months for 2 years (or until death) for survival (from the last day of treatment). Patients **without PD** at end of treatment will be followed every 6 months for 5 years (or until death) for survival and progression (from the last day of treatment). Follow-up may occur over the phone.
- j. Patients who are removed from study treatment for toxicity should be followed until toxicity resolves to grade 1 or baseline.
- k. Radiology assessment by CT or MRI will be done at Week 6, Week 12, Week 20 and every 8 weeks (+/- 7 days) thereafter. After 1 year of protocol treatment, patient may be switched to scans every 12 weeks (+/- 7 days) at the discretion of the patient and treating physician.
- l. Blood samples for mandatory correlative study will be collected at screening or on Cycle 1 Day 1 prior to treatment, and day 1 of Cycle 2, 3, and 4 , (+/-3 days) as in section 9.1.
- m. Unless otherwise noted, on-therapy windows for testing will be as follows: imaging scans should be completed within +/- 1 week of the target time point, and labs and physical examinations within +/- 3 days of the target time point.
- n. End of treatment visit must occur within 30 days following the last day of treatment, particularly prior to patient starting new treatment.
- o. Patient to call coordinator weekly to report toxicities- if no toxicities to be reported, patient need not call in. Toxicities should be followed for 30 days after last dose of study treatment, however, new toxicities that arise within the 30 day period definitely related to new anti-cancer treatment and NOT related to study treatment do not need to be reported.
- p. ONLY required for patients with prior anthracycline use OR otherwise at risk for left ventricular systolic dysfunction. May be assessed by MUGA or echocardiogram.

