- q. Day 1 of each cycle should be every 28 days. In the event that this day falls on a holiday or other such event, study team should use +/- 3 day window to complete pre-treatment procedures, and dispense protocol agents to patients with instructions to commence treatment on day 1. Any missed doses will not be made up and should be skipped to maintain a 28-day cycle.

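### The diaries' vomiting instruction sends the next topotecan dose to Day 22, in the topotecan-free week, when the patient vomits on Day 15

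*Combined protocol and SAP*

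**What the plan says.** Section 4.1 gives topotecan "on days 1, 8, and 15 of each 28 day cycle", and Sections 4.2 and 4.2.1 repeat that schedule. For a lost dose, Section 4.2.1 states: "If a dose is vomited or if a dose is missed for any reason, the dose should not be made up". Footnote q of the study procedures table agrees: "Any missed doses will not be made up and should be skipped to maintain a 28-day cycle".

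The topotecan diary in Appendix F has three numbered instructions. Item 1 describes weekly dosing for three weeks and adds: "On the fourth week you will not take topotecan". Item 3 deals with vomiting: "If you vomit on a day where you take both medications, you will take your next dose of topotecan one week later". The grid below it marks Days 16 to 28 with "DO NOT TAKE TOPOTECAN ON THESE DAYS".

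Item 2 of the pazopanib diary first covers pazopanib-only days: "If you vomit on a day where you only take pazopanib, the next dose would be the following day". It then repeats the same sentence about two-drug days. That page has no statement about week 4, and its grid records pazopanib only.

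**The concern.** The vomiting instruction has no exception for the last topotecan day of the cycle. On Days 1 and 8, a week later is the next scheduled dose. On Day 15 it is not, because the fourth week is the rest week.

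A patient who vomits on Day 15 therefore gets contradictory directions on the topotecan page. The sentence that speaks directly to vomiting is the one that is wrong for that day. On the pazopanib page nothing opposes it.

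Topotecan is an oral cytotoxic taken at home. Following the sentence would fill the rest week and give doses on Days 1, 8, 15, 22 and 29. Section 1.6 lists neutropenia among the phase I dose-limiting toxicities, and the recommended phase II schedule is Days 1, 8 and 15 every 28 days. The matter is one of patient safety and protocol adherence; no statistical quantity depends on it.

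**Working it through.** **Inputs.** Dosing days 1, 8 and 15 of a 28-day cycle, starting dose 8 mg (Sections 4.1 and 4.2). Reduced doses 6, 4 and 2 mg (Section 4.3). Diary rule: next topotecan dose = day of vomiting + 7 (Appendix F). Protocol rule: a vomited dose is not made up (Section 4.2.1). The plan states no figure of its own on this point.

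**Day arithmetic.**

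| Vomiting on | Diary rule (+7) | Next scheduled dose | Agreement |
|---|---|---|---|
| Day 1 | Day 8 | Day 8 | yes |
| Day 8 | Day 15 | Day 15 | yes |
| Day 15 | Day 22 | Day 29 (Day 1 of next cycle) | no |

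One of the three two-drug days is affected. Day 22 is in the fourth week, inside the grid's blocked range, and 29 − 22 = 7 days before the next scheduled dose.

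**Topotecan swallowed in the cycle at the starting dose.** Planned: 3 × 8 = 24 mg. If the diary sentence is followed after Day 15: 4 × 8 = 32 mg. Ratio 32/24 = 1.33. The ratio is the same at reduced doses: 24 against 18 mg, 16 against 12 mg, 8 against 6 mg.

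**Topotecan retained.** Let f be the share of the Day 15 dose kept down. The documents do not give f, so the full range is assumed.

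| f | Diary sentence followed, (3 + f) × 8 | Against planned 24 mg | Not made up, (2 + f) × 8 | Difference between rules |
|---|---|---|---|---|
| 0 | 24 mg | 0% | 16 mg | 8 mg |
| 0.5 | 28 mg | +16.7% | 20 mg | 8 mg |
| 1 | 32 mg | +33.3% | 24 mg | 8 mg |

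The trigger is vomiting on a day when both drugs are taken. It does not require that the topotecan dose was lost, so f = 1 is possible.

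**Blood counts.** Footnote h of the study procedures table gives the routine schedule: "Performed on day 1 and 15 of cycles 1 and 2 (+/- 3 days) then day 1 of each cycle". Day 22 therefore falls 22 − 15 = 7 days after the last routine count in cycles 1 and 2, and 22 − 1 = 21 days after it from cycle 3 onward, ignoring the visit windows. No routine count is due between Day 15 and the next Day 1.

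**The case against.** The best defence is that the sentence is a patient-level version of Section 4.2.1: do not retake the dose, wait for the next one. Read that way it is a correct rule that lacks one exception. On the topotecan page two explicit statements, item 1 and the grid, oppose a Day 22 dose. Most patients would also use that page to record any topotecan they take. This is fair, and it lowers the risk considerably. It does not remove the conflict, and it does not help a patient reading the pazopanib page.

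Other safeguards exist. Patients call the coordinator weekly if they have toxicities (footnote o), so a call about vomiting could fall before Day 22. Diaries are reviewed at visits and capsules are counted each cycle, though both detect an error only afterwards. The next Day 1 dose is conditional on blood counts (Section 4.3), and patients with significant cytopenias have counts more often (footnote h).

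The blood-count gap is weak support. Day 8 is never among the count-gated days in Section 4.3, and from cycle 3 the scheduled Day 8 and Day 15 doses also have no routine same-day count. What is unusual about a Day 22 dose is the lost rest week, not the interval since the last count.

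The 33% figure requires several things at once: vomiting on Day 15, following the vomiting sentence over item 1 and the grid, having spare capsules, and retaining the whole dose. That objection stands, and the figure should be read only as an upper bound.

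Finally, Appendix H records the study as closed to further accrual, so few patients, or none, may still be using the diaries.

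**Conclusion.** The inconsistency is real. The vomiting instruction in both diaries is wrong for Day 15 and contradicts the dosing schedule, the rule against making up doses, and the topotecan diary's own item 1 and grid.

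Its firm size is one unscheduled dose per occurrence, 8 mg at the starting dose. Against the planned 24 mg, the retained excess runs from 0% to 33%, depending on the assumed share of the Day 15 dose kept down. This presumes the patient has a further dose in hand; the number of capsules dispensed is not stated. The documents give no vomiting rate, so no expected frequency or average effect can be calculated.

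This is a minor patient-safety wording correction. It changes neither the primary endpoint nor the statistical design.

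**What to change.** In item 3 of the topotecan diary and item 2 of the pazopanib diary, replace the one-week wording with: *on your next scheduled topotecan day (after Day 15, this is Day 1 of the next cycle)*. This gives Day 8, Day 15 and Day 29 after vomiting on Days 1, 8 and 15 respectively, and it agrees with Section 4.2.1 and footnote q.

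Reissue both pages to any patients still on treatment; the documents do not say how many there are. The cost is one sentence on each of two diary pages, plus IRB approval of the revised patient-facing document.
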